10.	Possible device related Adverse Effects.....	10
11.	Special Populations.....	10
12.	Study device (Lumena mask) description.....	11
13.	"Lumena"- Specific Components.....	13
14.	Study Description.....	14
15.	Data Collected.....	16
16.	Risk-Benefit Assessment.....	17
17.	Confidentiality and Information Security.....	18
18.	Study Duration.....	19
19.	References.....	20

	Date 1 st Issued: 26.12.2021	
Title: Clinical trials protocol – “Lumena”; Safety and usability of the LUMENA non-invasive ventilation mask	Doc #: CL-003	Revision: 04
	Confidential	Page 5 of 20

1. Study Design:

A first-in-human, prospective, randomized, non-blinded cross-over study

2. Background:

The COVID-19 pandemic has taken the lives of millions of persons worldwide and disrupted the lives of countless more¹. Healthcare workers are considered to be at increased risk of contracting SARS-CoV-2, possibly due to increased and prolonged exposure to SARS-CoV-2 confirmed or suspected individuals².

Nosocomial spread of SARS-CoV-2 amongst patients and contagious spread to HealthCare Workers (HCWs) have posed a major challenge and risk for healthcare systems. In Italy, HCWs are have paid a heavy price in addition to their professional and humanitarian efforts, with 21,338 cases (more than 10,4% of total Italian cases and 154 deaths among physicians)³. Protecting healthcare workers from nosocomial infection is therefore of paramount importance in curbing the spread of the pandemic and in maintaining healthcare systems` capacity. To this aim, guidelines for protection of healthcare workers, including the use of Personal Protective Equipment (PPE) have been issued by several international^{4,5}.

SARS-CoV-2 is considered to spread via droplet distribution, however the presence of the virus in aerosols has been documented in experimental⁶ and real-life conditions in crowded, poorly ventilated hospital areas unrelated to aerosol generating procedures⁷. Such infections have been reported to be associated with aerosol-generating procedures such as positive pressure ventilation⁸. Several events of nosocomial infection with SARS-CoV-2 following to the use of inhalation devices and/or non-invasive ventilation have occurred in the Tel Aviv Sourasky Medical Center (TASMC) [Internal TASMC data].

	Date 1 st Issued: 26.12.2021	
Title: Clinical trials protocol – “Lumena”; Safety and usability of the LUMENA non-invasive ventilation mask	Doc #: CL-003	Revision: 04
	Confidential	Page 6 of 20

Patients presenting to the emergency department, or needing hospitalization, for a variety of medical conditions often require Non-Invasive Ventilation (NIV). These patients` condition often requires close and continuous support by a staff member, putting these staff members at increased exposure to respiratory aerosols which could possibly contain SARS-CoV-2 of other airborne pathogens.

The “Lumena” mask is a disposable, single-patient, adult Oro-nasal mask, intended to provide a patient interface for transmission of NIV while minimizing dispersion of bio-aerosols from and into the breathing surrounding. It makes use of a dual layered containment space being constantly depressurized into a filtration system, thus allowing safety of use with non-hermetically sealed devices.

The mask has been approved by the Israeli Ministry of Health ("AMAR" / אמ"ר) as a medical device based on its intrinsic properties. This mask has undergone pre-clinical testing and is approved for marketing in several authorities. Inspir Labs, the sponsor is ISO 13485 certified. The purpose of this study is to evaluate the safety, usability and effectiveness of the Lumena mask and its ability to prevent the spread of respiratory aerosols in a real-world clinical setting.

3. Study Objectives:

3.1. Primary objective:

To assess the safety of the Lumena mask, compared to commercially available, commonly used oro-nasal face masks.

3.2. Secondary objectives:

- 3.2.1. To assess the effectiveness of the Lumena mask in achieving pre-defined clinical endpoints (i.e. oxygenation and ventilation), compared to commercially available, commonly used oro-nasal face masks.

	Date 1 st Issued: 26.12.2021	
Title: Clinical trials protocol – “Lumena”; Safety and usability of the LUMENA non-invasive ventilation mask	Doc #: CL-003	Revision: 04
	Confidential	Page 7 of 20

- 3.2.2. To assess the effectiveness of the Lumena mask in reducing the spread of respiratory aerosol in the patient's environment, compared to commercially available, commonly used Oro-nasal face masks.
- 3.2.3. To assess patient comfort and satisfaction while using the Lumena mask, compared to commercially available, commonly used Oro-nasal face masks.
- 3.2.4. To assess staff ease of use and overall satisfaction with using the Lumena mask, compared to commercially available, commonly used Oro-nasal masks.
- 3.2.5. To assess the effectiveness of the Lumena mask in prevention of spread of respiratory particles during positive-pressure non-invasive ventilation within the Intensive Care Unit.

4. Sex:

Study will include both females and males, with at least 20% of patients being females.

5. Ages:

18 years and over

Title:

Clinical trials protocol – “Lumena”;

Safety and usability of the LUMENA non-invasive ventilation mask

Doc #: CL-003

Revision: 04

Confidential

Page 8 of 20

6. Number of patients:

6.1. 40 patients will be included in the study, until reaching 5 patients for each group.

Patients who drop out of the study for any reason will be replaced.

6.2. The study will be designed to contain 4 groups, each containing 5 patients.

6.3. The trial is designed as a crossover trial, as all patients will be required to use both Lumena mask and the control mask. The order of interventions is determined by the designated group. Prior to every inhalation and particle sampling, a baseline sample will be taken to filter possible carryovers from previous sampling.

Table 1 - Crossover Groups & Periods

Group	Period 1	Period 2	Period 3
A	Standard	Lumena No Suction	Lumena Suction
B	Standard	Lumena Suction	Lumena No Suction
C	Lumena No Suction	Lumena Suction	Standard
D	Lumena Suction	Lumena No Suction	Standard

	Date 1 st Issued: 26.12.2021	
Title: Clinical trials protocol – “Lumena”; Safety and usability of the LUMENA non-invasive ventilation mask	Doc #: CL-003	Revision: 04
	Confidential	Page 9 of 20

7. Statistical analysis:

Statistical analysis will be conducted following conclusion of the trial. A pre-test for the assumption of negligible carryover will be conducted as specified below:

$$T = \sqrt{\frac{mn}{N}} \frac{\bar{C}(X) - \bar{C}(Y)}{\sqrt{(SQ_{CX} + SQ_{CY}) / (N - 2)}}$$

After which a test for differences between treatment effects will be carried, according to the same formula but applying it to within-subject differences⁹

8. Inclusion Criteria:

- 8.1. Adults males and females aged 18 years and over.
- 8.2. Suffering from hypoxemic and/or hypercarbic respiratory failure requiring non-invasive ventilation and selected by medical staff to use CPAP or BiPAP.
- 8.3. Fully conscious (Glasgow Coma Scale 14-15) and able to cooperate with non-invasive ventilation.
- 8.4. Able to provide informed consent to participate in the study.
- 8.5. Have an active arterial line in place for arterial blood sampling (arterial lines will not be placed for the sole purpose of the study). Alternatively, IV line can be used.

9. Exclusion Criteria:

- 9.1. Age < 18 years.
- 9.2. Pregnancy.
- 9.3. Respiratory failure due to non-pulmonary pathology.

	Date 1 st Issued: 26.12.2021	
Title: Clinical trials protocol – “Lumena”; Safety and usability of the LUMENA non-invasive ventilation mask	Doc #: CL-003	Revision: 04
	Confidential	Page 10 of 20

9.4. Presence of a contraindication to the use of non-invasive ventilation or an absolute indication for invasive ventilation.

9.5. Presence of a facial deformity, heavy beard or moustache which prevents a good seal between the mask and the face.

9.6. Hemodynamic instability.

9.7. Severe upper gastrointestinal bleeding.

9.8. Chest trauma.

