The mask is connected via a standard suction tube to a vacuum source that can provide at least 30 liter/minute of flow as a safe, aerosol minimizing device, but can also be used as a regular, non-safe NIV mask when it is not connected to a vacuum source. The mask contains two separate spaces, an inner space positively pressurized to administer positive pressure ventilation, and a separate, negatively pressurized space that scavenges aerosol emitted during ventilation and prevents it from being released into the surrounding environment.

The mask has been approved by the Israeli Ministry of Health’s Medical Devices Department ("AMAR"/ר"מ), approval #34860001.

[figure not shown]

Figure 2: Lumena gap Pathway

Title:

Doc #: CL-003

Revision: 04

[figure not shown]
Clinical trials protocol – “Lumena”;

Confidential

Page 13 of 20

Safety and usability of the LUMENA non-invasive ventilation mask

13. "Lumena"- Specific Components:

The mask, which is available in 3 sizes (Small, Medium, Large), consists of the following basic components:

1. Mask Frame, containing:
 - a. Suction port for connection to a vacuum source, either wall suction or a portable vacuum machine using via a 28Fr suction tube in order to maintain negative pressure in the mask's outer layer
2. Clip On
3. Quick-Release Clip
4. Elbow
5. Oxygen Port Cap
6. Suction & Inlet Tubes Gripper (*2 in kit)
7. Swivel lock Ring
8. Head Cushion
9. Inner Cushion
10. Outer Cushion
11. Headgear Strap
12. O-Ring
13. Suction Cap
14. Silicone Guard

	Date 1 st Issued: 26.12.2021	
Title: Clinical trials protocol – “Lumena”; Safety and usability of the LUMENA non-invasive ventilation mask	Doc #: CL-003	Revision: 04
	Confidential	Page 14 of 20

14. Study Description:

14.1. Enrollment phase:

All patients at the relevant departments who require non-invasive mechanical ventilation according to treating physician's decision will be screened for eligibility, given an investigator is available. Study eligibility will be determined by the inclusion and exclusion criteria. All eligible patients who meet study eligibility will be offered to participate in the study. Signed informed consent will be performed by research staff.

The offer to enroll shall be presented only by the investigators and will be presented to all eligible patients.

Consented patients will be randomized to one of four groups. Each group has a unique sequence protocol:

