- A. 1) Standard NIV mask [30-60 minutes]; 2) Lumena mask without suction [30-60 minutes]; 3) Lumena mask with suction [30-60 minutes].
- B. 1) Standard NIV mask [30-60 minutes]; 2) Lumena mask with suction [30-60 minutes]; 3) Lumena mask without suction [30-60 minutes].
- C. 1) Lumena mask without suction [30-60 minutes]; 2) Lumena mask with suction [30-60 minutes]; 3) Standard NIV mask [30-60 minutes].
- D. 1) Lumena mask with suction [30-60 minutes]; 2) Lumena mask without suction [30-60 minutes]; 3) Standard NIV mask [30-60 minutes].

Data required for study purposes (see below) will be collected at time of enrollment from the medical record and/or from direct questioning of the study patient.

	Date 1 st Issued: 26.12.2021	
Title: Clinical trials protocol – “Lumena”; Safety and usability of the LUMENA non-invasive ventilation mask	Doc #: CL-003	Revision: 04
	Confidential	Page 15 of 20

14.2. Intervention phase:

Following randomization, each patient will be placed on BIPAP or a CPAP (per clinical need) using either the aerosol-reducing mask (Lumena) for approximately 1-2 hours, and then on the standard NIV mask used at the department for another 1-2 hours, or vice versa according to randomization scheme. In general, ventilation at each condition will be 30-60 minutes for each condition, with variation expected due to patient clinical need. Suction will be connected/disconnected from the Lumena mask according to the randomization schemes 30-60 minutes from placement of the mask. The patients will serve as their own control (cross over design).

During each of the three study phases (use of standard NIV mask, use of Lumina mask with suction and use of Lumina mask without suction), an inhalation of 5 ml 0.9% NaCl will be administered to the patient via the mask (using an in-line connector and a standard inhalation chamber) to enhance potential for environmental spread of small particles and thus enhance the ability to discriminate between the standard mask and the Lumina masks` ability to minimize aerosol spread.

Eligible patients will be enrolled into the study, perform trial activities and exit the study within a maximum of 1 day.

The study will be performed in a hospital intensive-care setting due to the nature of the device, and the required patients population.

	Date 1 st Issued: 26.12.2021	
Title: Clinical trials protocol – “Lumena”; Safety and usability of the LUMENA non-invasive ventilation mask	Doc #: CL-003	Revision: 04

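### Section 7's carryover pre-test cannot support the conclusion it is meant to support, does not fit the four-sequence, three-period layout, and has no stated consequence

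*Protocol*

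**What the plan says.** Section 7 announces the check: "A pre-test for the assumption of negligible carryover will be conducted as specified below". The printed statistic is a pooled-variance two-sample t on N-2 degrees of freedom, with group sizes m and n and group means of a quantity C in groups X and Y. The next step is: "After which a test for differences between treatment effects will be carried, according to the same formula but applying it to within-subject differences". C, X, Y, m and n are not defined, and no significance level, decision rule or alternative analysis is given.

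Section 6.3 and Table 1 set out four sequences of three conditions over three periods. In A and B the standard mask comes first; in C and D it comes last. Section 6.3 also plans a baseline sample before each inhalation and particle sampling, to filter carryover. On size, Section 6.1 says "40 patients will be included in the study, until reaching 5 patients for each group" and Section 6.2 says "The study will be designed to contain 4 groups, each containing 5 patients". These give 40 and 4 x 5 = 20. That conflict is a separate matter; both sizes are used below.

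**The concern.** The pre-test is offered as evidence for an assumption on which the within-patient comparison rests. Two features make it unfit for that. It compares totals between patients, so it is far less precise than the treatment test it is meant to protect. And it is a two-group formula placed on a design with four sequences and three conditions, so the carryover combination it tests is not the one that biases the mask comparison. A non-significant result could then be reported as reassurance while a bias of practical size remains. This touches the comparisons of oxygenation and ventilation (3.2.1), aerosol spread (3.2.2, 3.2.5) and comfort (3.2.3).

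**Working it through.** **Inputs.** From the protocol: the statistic and the order of the two tests (Section 7), the sequences (Table 1) and the group sizes (Sections 6.1 and 6.2). The protocol gives no power, alpha, effect size or SD, so there is no figure to reproduce. Assumed: normal data, total SD 1, two-sided alpha 0.05, within-patient correlation rho 0.3 to 0.9, and C as the patient total. The last is inferred from Section 7's contrast with within-patient differences.

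**1. Power of the pre-test.** For two conditions, totals have variance 2(1+rho) and differences 2(1-rho). A treatment effect t separates the groups' period differences by 2t; carryover c separates their totals by c. With c = t, the noncentrality of the pre-test divided by that of the treatment test is ½·√[(1-rho)/(1+rho)]. With 10 v 10 (18 df), 80% power needs noncentrality 2.963.

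| rho | ratio | pre-test noncentrality, c = t | power, c = t | power, c = t/2 |
|---|---|---|---|---|
| 0.3 | 0.367 | 1.087 | 17.8% | 8.1% |
| 0.9 | 0.115 | 0.340 | 6.2% | 5.3% |

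This is generous, because it lets the totals differ by the whole carryover. If only the standard mask leaves residue, step 2 shows that Standard-plus-suction totals differ by half of it, which is the last column.

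For a fixed difference in totals, power for rho 0.9 to 0.3 is:
- 0.5 SD: 8-10% with 10 v 10 and 12-16% with 20 v 20;
- 1 SD: 19-26% with 10 v 10 and 35-48% with 20 v 20.

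**2. What the pre-test tests in Table 1.** Let Ls, Ln and Lv be first-order carryover from Standard, Lumena without suction and Lumena with suction.

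| Sequence | carryover in Standard + suction total | carryover in suction minus standard |
|---|---|---|
| A | Ln | Ln |
| B | Ls | Ls |
| C | Ln + Lv | Ln - Lv |
| D | Ln | -Ln |

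- Pre-test contrast, A,B v C,D: (Ln+Ls)/2 - (2Ln+Lv)/2 = (Ls - Ln - Lv)/2.
- Bias of suction minus standard: [Ln + Ls + (Ln - Lv) - Ln]/4 = (Ls + Ln - Lv)/4.

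These are different combinations. Take one possible pattern, Ls = Ln = L and Lv = 0. Every sequence then has the same total, L, so the contrast is 0 while the bias is 2L/4 = L/2. On three-period totals the contrast is Ls - (Ln+Lv)/2 = L/2, which is not zero.

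**3. Simulation of that pattern** (no true mask effect, L = 0.5 or 1 SD, rho 0.5 or 0.8, 5 or 10 per group):
- pre-test on Standard-plus-suction totals rejects about 5%;
- pre-test on three-period totals rejects about 5-9%;
- bias is 0.25 or 0.50 SD;
- the following treatment test rejects about 15-61% with 5 per group and 30-97% with 10 per group.

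**4. Rejection for another reason.** With period effects p1, p2 and p3, the contrast on Standard-plus-suction totals also contains (p1 - p3)/2, because Standard is always first or last. Drift of 0.5 SD per period and no carryover raises rejection to about 9% (5 per group) or 13-14% (10 per group).

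**5. What the layout allows instead.** With patient, period and condition fitted, the least-squares weights for suction minus standard, in sixteenths and in period order, are A (-4, -2, 6), B (-4, 2, 2), C (2, 2, -4) and D (6, -2, -4). The squares sum to 56 + 24 + 24 + 56 = 160. At 5 per group the standard error is √[160/(256 x 5)] = 0.354 within-patient SD. The carryover bias is:
- Ls: (-2 + 2)/16 = 0;
- Ln: (6 + 2 - 4)/16 = 1/4;
- Lv: (2 - 4 - 2)/16 = -1/4.

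The bias is therefore (Ln - Lv)/4, or L/4 under the pattern above instead of L/2. Adding first-order carryover terms keeps everything estimable within patients. The standard error of suction minus standard rises from 0.354 to 0.374, and that of suction minus no suction from 0.316 to 0.400.

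**The case against.** Several points on the other side stand.

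- **No gate is written.** Section 7 only orders the two tests. Read literally, the treatment test always runs, and without carryover it keeps its level (simulated 4.7-5.1%). A reader might infer that a failed pre-test switches the analysis to period 1 and so inflates type I error. The protocol states no such switch, so that charge is not supported.
- **The exact blind spot is conditional.** It needs C to be the Standard-plus-suction total, and it needs equal residue from the two unsuctioned conditions with none from suction. A reader might take Section 12's remark that the mask "can also be used as a regular, non-safe NIV mask when it is not connected to a vacuum source" as showing this is the most plausible case. That sentence describes how the device can be used; it says nothing about residue.
- **There is a design safeguard.** The Section 6.3 baseline sample may reduce carryover in particle counts if the analysis uses it. Section 7 does not mention it, and it does not cover blood gases or comfort ratings.
- **Direction.** Under the illustrated pattern, residue raises the suction reading and understates the Lumena mask's benefit. It does not create a false claim of benefit in aerosol reduction.
- **The decision rule could sit in a SAP.** That is so, but the statistic and its purpose are fixed in the protocol, and the weakness lies there.

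**Conclusion.** The concern holds in a limited form. As printed, and with C read as patient totals, the pre-test cannot establish that carryover is negligible. It detects carryover equal to a treatment effect that the main test finds with 80% power only about 6-18% of the time (10 v 10, alpha 0.05, rho 0.9 to 0.3). Its two-group form does not track the bias in suction minus standard under Table 1. Low power holds on both readings of C examined. Power equal to alpha holds only for Standard-plus-suction totals under an assumed carryover pattern. SD, correlation and carryover size are all assumptions, because the protocol gives none.

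The documents do not support calling this a gate that distorts the type I error, or a test with no power in general. Severity is moderate: the primary objective is safety, the affected objectives are secondary, and Section 16 describes a feasibility proof-of-concept study.

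**What to change.** Replace the Section 7 paragraph as follows:

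- Delete the carryover pre-test.
- Make the comparison of conditions unconditional, in one within-patient model with condition and period over all three periods.
- For particle counts, use the Section 6.3 pre-inhalation baseline in that analysis.
- Report a first-order carryover term, estimated within patients, as a sensitivity estimate with its confidence interval, never as a condition for the main comparison.

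This needs one paragraph and no new data. The main estimate can still carry some carryover bias, (Ln - Lv)/4 for suction minus standard, which is why the sensitivity estimate should be shown beside it. Its price is precision: at 20 patients the standard error rises by 0.374/0.354 - 1 = 6% for suction minus standard and by 0.400/0.316 - 1 = about 26% for suction minus no suction.

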	Confidential	Page 16 of 20

14.3. Monitoring:

During all phases of the study (either using standard NIV mask or Lumina mask), a staff member will be present in the patient's room.

Vital signs during NIV will be recorded in real time by the staff member.

Before, during and after NIV, and electrocardiogram (ECG) will be monitored and arterial blood\ venous gas (ABG\VBG) samples will be drawn.

A particle-measuring device (Particle Plus 8303) will be placed at a distance of 1.5 meter from the patient`s face to record the level of aerosol spread.

Following each session of NIV, the patient as well as the staff member treating the patient will be asked to complete a short questionnaire regarding the comfort and ease of use of each of the masks used. Any adverse events will be captured in real time by the staff member.

15. Data Collected:

15.1. Demographics including as age, sex, DOB, height, weight and body mass index.

15.2. Past medical history including smoking status, co-morbid conditions and medication use.

15.3. Vital signs before, during and after non-invasive ventilation such as: heart rate, respiratory rate, Tidal volume, oxygen saturation, Mode of ventilation, peak Inspiratory Pressure, Pressure Support, Ventilator type and model, Trigger sensitivity, Fio2%, PEEP, blood pressure (invasive and/or non-invasive), and temperature.

15.4. Electrocardiogram (ECG) diagrams before use (historical ECG can be also use) and monitoring during use.

Title:

Doc #: CL-003

Revision: 04

Clinical trials protocol – “Lumena”;
 Safety and usability of the LUMENA non-invasive ventilation mask

Confidential

Page 17 of 20

- 15.5. Arterial blood\ Venous blood gas analysis for O₂, CO₂, pH and HCO₃ as well as serum Lactate levels before, during and after non-invasive ventilation. A maximum of 20 ml of blood will be collected from each patient.
- 15.6. Symptoms and signs during use of non-invasive ventilation (e.g. diaphoresis, anxiety).
- 15.7. Estimation of patient preference of the mask- The question shall be phrased thusly: which mask do you prefer?
- 15.8. Estimation of staff comfort (an analog 1-5 scale as well as recording of verbal comments) – the question shall be phrased thusly: In a scale of 1-5, 1 being very uncomfortable and 5 being very comfortable, how would you rate the mask?
- 15.9. Estimation of staff use - The question shall be phrased thusly: which mask do you prefer?

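### Section 7 fixes a two-group crossover t statistic for a design with four sequences, three periods and three conditions, and the result depends on which groups and which difference are chosen

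*Protocol*

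**What the plan says.** Section 7 says: "A pre-test for the assumption of negligible carryover will be conducted as specified below". It then prints a pooled two-sample t statistic with groups X and Y, sizes m and n, and N − 2 degrees of freedom. None of these symbols is defined. The treatment comparison follows: "After which a test for differences between treatment effects will be carried, according to the same formula but applying it to within-subject" differences. The section does not say which difference.

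The design is larger than two groups. Section 14.1: "Consented patients will be randomized to one of four groups. Each group has a unique sequence protocol". In Table 1 and 14.1, sequences A and B start with the standard mask and then use Lumena in both modes. C and D use both Lumena modes first and end with the standard mask. C, for example, is "1) Lumena mask without suction [30-60 minutes]; 2) Lumena mask with suction [30-60 minutes]; 3) Standard NIV mask [30-60 minutes". The standard mask is therefore in period 1 or period 3, never in period 2.

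Section 14.2 describes the course in two blocks, Lumena "and then on the standard NIV mask used at the department for another 1-2 hours, or vice versa according to randomization scheme". For particle counts, section 6.3 adds: "Prior to every inhalation and particle sampling, a baseline sample will be taken to filter possible carryovers from previous sampling".

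**The concern.** The printed statistic belongs to a crossover with two sequences and two periods. There, X and Y are the two orders and each patient has only one difference. Here there are four orders, and each patient has three pairwise differences plus the pooled one. Two analysts could follow section 7 faithfully and reach different estimates.

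At stake are the quantitative comparisons with the standard mask: oxygenation and ventilation (3.2.1), aerosol spread (3.2.2) and the staff comfort rating in 15.8, taken on "an analog 1-5 scale as well as recording of verbal comments". The possible readings differ in exposure to period effects, in power and in the effect they estimate.

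**Working it through.** **Inputs.** The sequences come from Table 1 and 14.1, and the statistic from section 7. The number of patients is 20 (5 per sequence, 6.2); 6.1 also says 40, so 10 per sequence was run as well. The protocol gives no SD, test level or period effect. Assumed: normal errors, within-patient SD 1, two-sided 5% test. There is no figure in the plan to reproduce.

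**Step 1: period terms in each within-patient difference.** Let p1, p2, p3 be the period effects.

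| Sequence | Standard − Lumena with suction | Standard − Lumena without suction |
|---|---|---|
| A | p1 − p3 | p1 − p2 |
| B | p1 − p2 | p1 − p3 |
| C | p3 − p2 | p3 − p1 |
| D | p3 − p1 | p3 − p2 |

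**Step 2: the readings.**

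- *(a) A+B v C+D, standard v one Lumena mode.* The A, B mean is p1 − (p2 + p3)/2 and the C, D mean is p3 − (p1 + p2)/2. The estimate averages the two, so its bias is (p1 − 2·p2 + p3)/4.
- *(b) Same groups, standard v the mean of both modes.* The bias is the same, because both columns have the same group means.
- *(c) Mirror pairs, A v D for suction and B v C for no suction.* (p1 − p3) + (p3 − p1) = 0, so there is no period bias.
- *Suction v no suction (A+C v B+D).* The period terms cancel.

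**Step 3: type I error at n = 20** (40,000 simulated trials per setting).

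| Period effects (SD) | Bias, standard − Lumena | (a) | (b) |
|---|---|---|---|
| Linear, 0.25 to 1 per period | 0 | about 4–5% | 5% |
| 0, 0.5, 0.75 | (0 − 1 + 0.75)/4 = −0.0625 | 5.2% | 5.5% |
| 0, 0.5, 0.5 | (0 − 1 + 0.5)/4 = −0.125 | 6.5% | 7.3% |
| 0, 1, 1 | (0 − 2 + 1)/4 = −0.25 | 10.3% | 14.0% |

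With 40 patients, the 1 SD step gives 17.5% and 24%.

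**Step 4: variance and power at n = 20.**

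- (a): ¼(2/10 + 2/10) = 0.100; power about 85% for a 1 SD difference without period effects.
- (b): ¼(1.5/10 + 1.5/10) = 0.075. A 1 SD effect with suction only is estimated as (1 + 0)/2 = 0.50, with 41% power.
- (c): ¼(2/5 + 2/5) = 0.200; power about 50% for 1 SD.
- Least squares with patient, period and condition: 60 observations − 24 parameters = 36 df. Variance of one Lumena mode v standard is 0.125, power about 79% for 1 SD, and type I error about 5% under every shape tried.

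**Step 5: the carryover pre-test.** On totals of standard plus one Lumena mode (or plus the mean of both), A+B minus C+D is [p1 + (p2 + p3)/2] − [p3 + (p1 + p2)/2] = (p1 − p3)/2. A plain time trend could then look like carryover. On three-period totals every sequence gives p1 + p2 + p3 and nothing remains. Mirror-pair totals (A v D, B v C) are p1 + p3 in both groups, so again nothing remains.

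**The case against.** **Left to the SAP.** Defining groups and contrasts is ordinary SAP content, and the SAP is not shown. This stands for missing detail. It does not answer the mismatch, because section 7 itself commits to a two-group formula; an SAP would have to choose a reading or depart from it.

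**The bias depends on the reading.** Section 14.2 describes mask placement, not analysis, and mirror pairs apply the formula without period bias. This stands. The price of mirror pairs is half the patients per comparison.

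**Pooling is a choice of estimand.** Averaging the Lumena modes is not an error in itself. That is fair, but the protocol does not say that it wants the average.

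**Adjustment can cost accuracy.** For a 0.5 SD step at n = 20, reading (a) has mean squared error 0.100 + 0.125² = 0.116, below the adjusted 0.125. Break-even is a step s with (s/4)² = 0.025, so s is about 0.63 SD. This stands as a trade-off for a study that calls itself a feasibility proof of concept.

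**Particle counts have a baseline.** The sample in 6.3 may remove some drift. It is described only for inhalation and particle sampling, and a per-period baseline for blood gases is not clearly described in 14.3 or 15.5.

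**Conclusion.** The mismatch between section 7 and the design is certain and should be corrected. The size of any bias is conditional: it needs the A+B v C+D reading and a non-linear period effect. At n = 20, type I error is about 5% for linear or mildly curved trends and 10–14% for a 1 SD step after period 1. The halving of a suction-only effect under pooling needs no period effect.

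A reader might infer more than the documents support:

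- *Severe error inflation.* An effect of 1 SD in period 2 only would give 28% (a) or 41% (b) at n = 20, but nothing in the protocol makes that shape likely.
- *A pre-test that always confuses time trend with carryover.* This holds for two-condition totals over A+B v C+D, not for three-period totals or mirror pairs.
- *Damage to all outcomes.* Adverse events (15.11, the primary safety objective) and mask preference (15.7, 15.9) are not affected. Item 15.10 is worded for the experimental mask only, so it is not a settled comparison with the standard mask. Suction v no suction is not biased when tested as A+C v B+D.

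**What to change.** For quantitative outcomes, replace the section 7 formula with wording such as:

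> Condition differences will be estimated from a linear mixed model with condition (standard, Lumena without suction, Lumena with suction) and period (1, 2, 3) as fixed effects and patient as random effect, with Kenward-Roger degrees of freedom. Contrasts: Lumena with suction v standard; Lumena without suction v standard; Lumena with suction v without suction. The model assumes negligible carryover.

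Least squares with fixed patient effects (36 df at n = 20) is an equivalent choice for complete data. The small-sample method should be named: a check of the mixed model on 800 simulated trials gave type I error of 5.5% and 6.6% (Monte Carlo SE 0.8 points).

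Drop the two-group carryover pre-test. Do not use the pre-inhalation particle sample as a covariate unless it is taken before that period's mask and suction are in place; 14.2 says "an inhalation of 5 ml 0.9% NaCl will be administered to the patient via the mask", so the sample may already reflect the condition. For the ordinal 1–5 rating the model is approximate. Adverse events and preference stay outside it.

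The cost is wording only, with no new data. Without period effects at n = 20, the variance against reading (a) rises from 0.100 to 0.125, so the SE is √1.25 = 1.12 times as large and power for a 1 SD difference is about 79% instead of 85%. Against reading (b), if both modes differ equally from standard by 1 SD, each separate contrast has about 79% power instead of 93%. Suction v no suction loses no precision: its SE is 0.316, and 0.316² = 0.100 is also the variance of the A+C v B+D test.
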